#### **10.6 Secondary Endpoints**

##### **10.6.1 Antibody Formation**

Binding antibody formation will be assessed at pre-dose and at EOS. Antibody data will be summarized and listed for each subject.

##### **10.6.2 Pharmacokinetic Parameters**

The PK concentration analysis set will be used for the analysis of the PK endpoints.

Biostatistics will provide the ADPC dataset to CPMS for PK analyses. All PK analyses specified in this section will be performed by CPMS.

Individual plasma concentration-time plots for etelcalcetide will be presented graphically for each subject as well as mean (SE) concentration-time plots for each cohort. PK parameters will be estimated using non-compartmental analysis (NCA) using Phoenix WinNonlin Software (Certara, Princeton, NJ). Actual dosing and sampling times will be used for calculation of PK parameters. Descriptive statistics will be generated for each PK parameter if data allows.

##### **10.6.3 Pharmacodynamic Parameters**

For concentrations of serum iPTH and serum calcium (total calcium, albumin corrected calcium, and ionized calcium) over time, the absolute value and percent change from baseline at each post-baseline time point will be summarized by cohort and overall.

Individual and mean (SE) of the absolute value, change from baseline and percent change from baseline at each post-baseline time point will be plotted. A combined plot with plasma concentration for etelcalcetide and iPTH concentration over time may be provided.

##### **10.6.4 Subject Incidence of TEAE**

The subject incidence of AEs will be summarized for all treatment-emergent AEs, serious AEs, AEs related to investigational product, and fatal AE.

The number and percentage of subjects will be tabulated by system organ class (SOC) and preferred term (PT). The TEAEs will also be presented by worst CTCAE grade. This also includes summary of subject incidence of TEAEs with grade  $\geq 3$  or  $\geq 4$  overall and by SOC and PT. Subject incidence of EOIs will be summarized according to the EOI

search strategy categories defined by the EOI steering committee unless otherwise specified (see below).

- Torsade de pointes-QT prolongation [Standard MedDRA Query (SMQ)]
- Ventricular tachyarrhythmias [SMQ])
- Convulsions (SMQ)
- Hypersensitivity (SMQ)
- Hypocalcemia (EOI)
- Hypophosphatemia (EOI)
- Infusion reaction (EOI) : only include events with onset day coincide with IP infusion and resolved on the same day or the day after onset.

All adverse event tables will be summarized by cohort and overall. Details of each adverse event will be listed.

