**Treatment-Related AE:**

A treatment-related AE is any treatment-emergent AE that per investigator's review has a reasonable possibility of being caused by the investigational product.

Baseline

For any variable, unless otherwise defined, baseline is the last assessment taken prior to the first investigational product administration.

Baseline iPTH, cCa, total calcium, ionized calcium are defined as the average of screening and Day -2 assessments. If not all the values are available, the average will be calculated based on available value(s).

Baseline pre-dialysis ECG parameters including PR, QRS, QT, QTcB and QTcF are defined as the average of last non-missing pre-dialysis screening assessment and Study Day -2 pre-dialysis assessment.

---

The use of concomitant medication of interest at baseline is defined as use of each concomitant medication on Study Day 1. This includes medication use that starts prior to Study Day 1 and ends on Study Day 1 or duration of use covers Study Day 1.

Change from Baseline

The arithmetic difference between a post-baseline value and the baseline value:

Change (absolute) from Baseline = (Post-baseline Value – Baseline Value)

Percent change from Baseline

Percent Change from Baseline = [(Post-baseline Value – Baseline Value) / Baseline Value] x 100

Body Mass Index (BMI)

BMI will be calculated as weight (kg)/ [height (m)] in the clinical database.

Corrected (Bazett) QT Interval (QTcB)

The Bazett correction will be calculated from the investigator reported QT (msec) and RR interval (msec) (QTcB=QT/(RR/1000)0.50).

Corrected (Fridericia) QT Interval (QTcF)

The Fridericia correction will be calculated from the investigator reported QT (msec) and RR interval (msec) (QTcF=QT/(RR/1000)0.33).

End-of-Study

The EOS is the last planned clinical visit for each subject enrolled in this study. The last planned visit day for subjects in cohort 1 and 2 is on Study Day 30.

Subject-level End of Study (EOS) Date

End of study for each subject is defined as the date the subject last participated in the study. The date will be recorded on the End of Study CRF page.

Enrollment

A subject will be considered enrolled when the Investigator decides that the subject has met all eligibility criteria. Enrollment Date is defined as the date collected on the CRF.

Investigational Product

The term investigational product is used in reference to etelcalcetide.

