### **9.3 Handling of Missing and Incomplete Data**

The following imputation for missing or incomplete data will be performed if required:

- Incomplete or missing adverse event and concomitant medication dates will be imputed as described in [Appendix B](#). If imputed dates are used, then they will be identified as such in the final study report.
- PK concentrations below the lower limit of quantification will be omitted from PK parameter estimates.

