## Appendix B. Handling of Missing or Incomplete Dates for Adverse Events and Concomitant Medications

### Imputation Rules for Partial or Missing Stop Dates

If the month and year are present, impute the last day of the month. If only the year is present, impute December 31 of that year. If the stop date is entirely missing, impute it with EOS date. If a partial or complete stop date is present and the 'ongoing' or 'continuing' box is checked, then it will be assumed that the AE or conmed stopped and the stop date will be imputed, if partial.

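### The infusion-reaction event-of-interest row can undercount: it leaves out Day 1 reactions lasting past Day 2 and nearly all with no recorded stop date

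*SAP*

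**What the plan says.** SAP section 6 names seven categories of adverse event of interest, and SAP 10.6.4 says how each is found. Infusion reaction is the only one with a timing and duration condition: "only include events with onset day coincide with IP infusion and resolved on the same day or the day after onset". The SAP gives no reason for the resolution part. The other six categories have no such condition.

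SAP 9.3 brings adverse event dates under the imputation rules: "Incomplete or missing adverse event and concomitant medication dates will be imputed as described in" Appendix B. That appendix has three rules for stop dates:

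- entirely missing: "If the stop date is entirely missing, impute it with EOS date";
- day missing: "If the month and year are present, impute the last day of the month";
- day and month missing: "If only the year is present, impute December 31 of that year".

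On the end-of-study date, SAP section 6 states: "The last planned visit day for subjects in cohort 1 and 2 is on Study Day 30". At subject level it adds: "End of study for each subject is defined as the date the subject last participated in the study". A subject who withdraws therefore has an earlier date.

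The SAP makes no exception to Appendix B for the infusion-reaction row and plans no second count without the resolution condition. The other summaries have no duration limit: "The subject incidence of AEs will be summarized for all treatment-emergent AEs, serious AEs, AEs related to investigational product, and fatal AE". SAP 10.6.4 also plans tables by worst grade and a listing of every event.

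**The concern.** Onset on the day of infusion already ties the event to the dose. The resolution condition then selects on how the event turned out, and it removes the more prolonged reactions. Appendix B adds a second loss. When the stop date is blank, the imputed date is late by design, and here a late date means exclusion. A reaction that lasted an hour but was never given a stop date is treated like one that lasted a month.

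The cut-off also falls where dates are likely to be weakest. Subjects may leave after the 4-hour sample on Day 1 and next attend on Day 3 (Protocol synopsis, Treatment Period; Protocol Table 1). Whether a reaction ended on Day 2 will often rest on later report.

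What is at stake is the one row that groups different preferred terms as infusion reactions, for an intravenous product not previously studied in children (Protocol 2.3). If two children react and the events are coded to different terms, the term-level tables show two single events. Neither term reaches the two-subject threshold for a common event in SAP section 6.

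**Working it through.** The plan gives no figure to reproduce here, so the check is to apply the stated rules to an event that starts on Day 1.

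**Inputs.** Onset is Day 1, the only dosing day. The event enters the row if stop date − onset date ≤ 1 day (SAP 10.6.4). Stop-date imputation follows SAP Appendix B. Planned end of study is Day 30 (SAP section 6). The minimum sample is 10 overall and 5 per cohort (SAP 3.2).

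**Rule applied.**

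| Stop date on record | Stop date used | Days after onset | In the row? |
|---|---|---|---|
| Day 2 | Day 2 | 2 − 1 = 1 | Yes |
| Day 3 | Day 3 | 3 − 1 = 2 | No |
| None, end of study Day 30 | Day 30 | 30 − 1 = 29 | No, whatever the dosing date |
| None, end of study Day 2 | Day 2 | 2 − 1 = 1 | Yes |
| Month and year only, dosing month | Last day of that month | Depends on dosing date | Only if dosed on the last two days of the month |
| Year only, dosing year | 31 December | Depends on dosing date | Only if dosed on 30 or 31 December |

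**Share of calendar dates that pass.**

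- Entirely missing, end of study Day 30: 0 of 365 (0 of 366 in a leap year).
- Month and year only: 12 months × 2 days = 24 dates. 24/365 = 6.6% (also 6.6% of 366), so about 93% fail.
- Year only: 2 dates in the year.

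An entirely missing stop date passes only if the subject's own end-of-study date is Day 1 or Day 2.

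**Effect of one affected subject at the minimum sample.**

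- Overall: 1/10 = 10% by onset alone; 0/10 = 0% under the current rule.
- In a cohort: 1/5 = 20% by onset alone; 0/5 = 0% under the current rule.

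**Record or episode.** Protocol 9.2.1 calls for a separate event record at each severity level. The SAP does not say whether resolution is judged on a record or on the whole episode. Suppose a reaction lasts five days and changes from Grade 2 to Grade 1 on Day 2. It could enter the row through its first record. A five-day reaction at constant Grade 1 could not. The less severe of two equally long reactions would be the one left out.

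**The case against.** A reader might infer that these reactions disappear from the safety results. The documents do not support that. The treatment-emergent definition in SAP section 6 has no resolution criterion. The event stays in the all-event and worst-grade tables, in the related, serious and fatal tables where it qualifies, and in the listing. If its preferred term occurs in two or more subjects, it is also in the primary common-event table. It loses one label.

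A reader might also infer that only terms in the hypersensitivity query could surface elsewhere as events of interest. That cannot be shown. There are five further categories, and the search strategies are set by a steering committee and are not in the documents.

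Nor is it strictly true that every long reaction, or every one with an unknown stop date, is excluded. The split-record case and the few passing dates above are exceptions.

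Three further objections carry weight:

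- An onset-and-duration window is a plausible way to keep a broad term search specific. This stands, and is why the limited row should stay.
- SAP 9.3 imputes only where needed and does not say that an imputed date decides resolution for this row. This stands as an ambiguity. It does not rescue the count, because an event with no stop date does not show resolution by Day 2 without imputation either. The SAP has to say what happens.
- Investigators must record resolution dates and follow events (Protocol 9.2.1), so missing dates may be few. This is fair, and the documents give no frequency.

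Finally, no decision uses this row. The stopping rules rest on related events by grade and on serious events (Protocol 6.2.2). The Cohort 2 review uses all available data (SAP 8), and no hypothesis is tested (SAP 5).

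**Conclusion.** The concern holds for the infusion-reaction row in SAP 10.6.4 and no further. As written, the row leaves out Day 1 reactions lasting past Day 2, unless a change of grade splits the record. With Appendix B, it also leaves out nearly all Day 1 reactions that have no recorded stop date, brief ones included. Both losses make the row look more favourable.

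The size is one subject at a time: 10 percentage points overall or 20 in a cohort, at the minimum sample. That is the arithmetic of small denominators. It does not estimate how often this will happen, which the documents do not allow. The conclusion assumes that imputed dates feed the row, as SAP 9.3 and Appendix B read most naturally, and that the subject is followed beyond Day 2. It is a minor point of specification in a secondary safety table and worth correcting because the correction is cheap.

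**What to change.** Amend SAP 10.6.4 to report two rows:

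1. **Onset-only row:** events found by the prespecified infusion-reaction search with onset on the day of infusion, whatever their duration.
2. **Resolution-limited row:** the present definition, with three clarifications. The resolution condition is applied to recorded stop dates only, never to imputed ones. An event with a missing stop date that is not recorded as ongoing is counted as included. Resolution is judged per episode, not per severity record.

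The listing should show duration and mark imputed dates.

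The cost is a short addition to the SAP and a flag in the program, with no new data collection. The downside is that a few longer Day 1 events unrelated to the infusion may enter the onset-only row. Appendix B also sets some missing or partial start dates to the dosing date, so those events could enter it too. The listing will show both, and the limited row beside it keeps the more specific count.

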#### **10.7 Other Safety Endpoints**

##### **10.7.1 Exposure to Investigational Product**

Subject listing of manufacturing lot numbers and a separate listing of unique manufacturing lot numbers used in this study will be provided. Details for each etelcalcetide administration will be listed for every subject.

##### **10.7.2 Exposure to Concomitant Medication**

All medications will be coded using the World Health Organisation Drug (WHO DRUG) dictionary. A subject listing of concomitant medications during the study will be presented.

The count and percentage of subjects receiving the following selected medications: nutritional vitamin D (vitamin D supplement), vitamin D sterol (active vitamin D), calcium supplements, and phosphate binder will be summarized by cohort and overall at baseline and during the study.

The number and proportion of subjects with each dialysate calcium concentration at baseline will be summarized. Summary of changes in dialysate calcium concentration during the study will be provided if data allows.

#### **11. Changes From Protocol-specified Analyses**

There are no changes to the protocol-specified analyses.

---

**12. Literature Citations / References**

Not applicable.

---

13. Appendices

---

#### **Appendix A. Reference Values / Toxicity Grades**

For CTCAE grading system V4.0, please refer to:

[http://evs.nci.nih.gov/ftp1/CTCAE/CTCAE\\_4.03\\_2010-06-14\\_QuickReference\\_5x7.pdf](http://evs.nci.nih.gov/ftp1/CTCAE/CTCAE_4.03_2010-06-14_QuickReference_5x7.pdf)

## Appendix B. Handling of Missing or Incomplete Dates for Adverse Events and Concomitant Medications

### Imputation Rules for Partial or Missing Stop Dates

If the month and year are present, impute the last day of the month. If only the year is present, impute December 31 of that year. If the stop date is entirely missing, impute it with EOS date. If a partial or complete stop date is present and the 'ongoing' or 'continuing' box is checked, then it will be assumed that the AE or conmed stopped and the stop date will be imputed, if partial.

### Imputation Rules for Partial or Missing Start Dates

		Stop Date						
		Complete: yyyymmdd		Partial: yyyy-mm		Partial: yyyy		Missing
Start Date		<1 st Dose	≥1 st Dose	<1 st Dose yyyy-mm	≥1 st Dose yyyy-mm	<1 st Dose yyyy	≥1 st Dose yyyy	
Partial: yyyy-mm	=1 st Dose yyyy-mm	2	1	2	1	N/A	1	1
	≠ 1 st Dose yyyy-mm		2		2	2	2	2
Partial: yyyy	=1 st Dose yyyy	3	1	3	1	N/A	1	1
	≠ 1 st Dose yyyy		3		3	3	3	3
Missing		4	1	4	1	4	1	1

1 = Impute the date of first dose

2 = Impute the first of the month

3 = Impute January 1 of the year

4 = Impute January 1 of the stop year

Note: For subjects who were never treated (first dose date is missing), partial start dates will be set to the first day of the partial month.

Note: If the start date imputation leads to a start date that is after the stop date, then do not impute the start date.
